4.3.6 Arterial blood gas

An arterial blood gas sample will be drawn from a subject's radial artery using standard technique as per the study center's Standard Operating Procedure if a subject experiences an acute dyspnea episode (Refer to Table 3).

PCO₂, PO₂, and pH should be recorded on the pCRF.

4.3.7 Cycle exercise testing

Cycle exercise testing will be performed using methodology described by O'Donnell et al. (O'Donnell, 1998; O'Donnell, 1993)^{4,5}. Minute ventilation (V_E), tidal volume (V_T), oxygen saturation (SaO₂) by pulse oximetry, and oxygen uptake (VO₂) will be monitored throughout exercise testing and during exercise recovery.

On Study Day 4 of Periods I and II, an incremental cycle exercise test will be performed to a symptom-limited maximum (maximum work capacity). Refer to Table 2 for specific time.

4.3.7.1 Testing equipment

Exercise testing will be conducted using a cardiopulmonary exercise testing system and an electronically braked cycle ergometer, with a constant pedaling frequency of 50-70 revolutions per minute (rpm). Subjects will breath through a mouthpiece attached to a low resistance flow transducer. This mouthpiece and valve setup will be adjusted to a fixed height for each subject, thus ensuring a relatively fixed position of the torso. Oxygen saturation by pulse oximetry and electrocardiographic monitoring will also be carried out continuously throughout testing.

The cycle ergometer should have a range of at least 0-600W with an accuracy of 2% or 3W above 25W. Calibration of the cycle ergometer should be performed within 2 weeks prior to the study. In addition, calibration of the cycle ergometer should be performed if the cycle is moved or when unusual response profiles raise concerns about the equipment.

4.3.7.2 Subject preparation

Subjects should not eat for at least 2hours before any exercise challenge. Subjects should dress appropriately for the exercise challenge. On arrival in the laboratory, a detailed explanation of the testing procedure and equipment should be given to the subject, outlining the risks and potential complications.

Before exercise, ECG electrodes will be carefully placed and secured after preparing the skin to ensure good recordings (if necessary, the area of the electrode placement should be shaved). Just prior to exercise, the subject will be informed that it is acceptable to swallow with the mouthpiece in place and that he/she must signal any unexpected difficulty, i.e., the subject is advised to point to the site of discomfort if chest or leg pain is experienced. A signal, such as a wave, should also be used when the subject wishes to terminate the test. Good communication with the subject throughout the whole procedure will increase the subject's confidence and helps to ensure a good effort.

Seat height should be adjusted so that the subject's legs are almost completely extended when the pedals are at the lowest point and the cycling rhythm practiced. When the subject is seated comfortably at the desired seat height, the distance between the seat and the floor will be measured and recorded. The same seat height will be used in Periods I and II for the subject.

4.3.7.3 Symptom-limited incremental cycle exercise test

Before exercise, while seated comfortably on the cycle ergometer, the subject will breathe for 3 minutes through the mouthpiece with nose clips in place. V_E , V_T , and VO_2 will be measured throughout the exercise test. Oxygen saturation by pulse oximetry and electrocardiographic monitoring of heart rate (HR) will be carried out throughout the testing. All variables will be recorded as 30 second averages at each work load and values at end-exercise (last 30 seconds of exercise).

The initial work rate will be set at 0 watts (i.e., loadless pedaling). The subject will perform 1 minutes of loadless pedaling prior to increasing the work rate. The subject will begin to pedal at 50-70 rpm and will be encouraged to maintain this pedaling frequency throughout the exercise challenge. The subject is encouraged to continue exercise for as long as possible (i.e., to exhaustion or maximal exercise).

At the end of each minute, the work rate will be increased in increments of 15 watts.

The subject will exercise until:

- Limited by symptoms (i.e., is unwilling to continue exercising because of discomfort associated with the exercise); OR
- Unable to maintain a pedaling frequency of at least 40 rpm despite continued encouragement to increase the frequency to 50-70 rpm; OR
- Unable to continue safely (in the opinion of the supervising technician).

At the end of the exercise, the time of exercise is recorded (minutes and seconds): time from the start of loaded pedalling to the end of exercise. Work capacity (Wcap) is defined as the highest work rate that is maintained for at least 30 seconds. During recovery, the subject is told to continue with no external workload (i.e., loadless pedaling) for at least 2 minutes to prevent fainting and to accelerate lactate removal.

Immediately upon completion of the exercise test, subjects will rate the discomfort with breathing at maximal exercise using the modified Borg Scale. Subjects will also perform an IC (inspiratory capacity) maneuver within 15 seconds of the end of exercise. ECG monitoring will continue for 5-10 minutes during the recovery period. Heart rate will be recorded from the ECG at various intervals (i.e., 1, 2, 3, 5, 7 and 10 minutes) during recovery.

Reasons for stopping the test for safety reason must be clearly established and known by all personnel involved in testing. These include:

Symptoms such as:

- acute chest pain;
- sudden pallor;
- loss of coordination;
- mental confusion;
- extreme dyspnea;

and signs such as:

- clinically significant abnormalities in ECG recordings during exercise, i.e., ST segment depression of > 0.1 mV, T-wave inversion, sustained ventricular tachycardia, polymorphic and/or frequent premature ventricular beats;
- fall in systolic pressure below resting value or about 20 mmHg below its highest value during exercise;
- hypertension > 200 mmHg systolic or > 100 mmHg diastolic

If the exercise has been stopped for one of these reasons, the subject should be monitored in the laboratory until signs/symptoms/ECG modifications have completely resolved. Full CPR equipment should be available in the laboratory.

4.3.7.4 Additional procedures for exercise testing

The following procedures for exercise testing should be observed to reduce exercise performance variability.

Pre-exercise diet: Subjects will fast 4 hours following study drug administration on Study Day 4. Water will be allowed to beginning 2 hours after study drug administration and volunteers should be encouraged to drink water in order to maintain an adequate hydration state. Immediately upon completion of the fast, subjects will be served lunch. Subjects will not be allowed to eat again until after completion of the cycle exercise test. Fluids are to be encouraged during this time.

Previous exercise: Subjects should be encouraged to stay well-rested and to refrain from any strenuous, fatiguing or exhausting activities (i.e., walking up flights of stairs) on the morning of the exercise test. Very strenuous, heavy type of activities, especially activities to which the volunteer is unaccustomed, can lead to muscle soreness 24-48 hours after the activity. Subjects should be encouraged to refrain from any heavy lifting, exhaustive digging in the garden, etc. for 2-3 days prior to each clinic visit, especially if the subject has not performed these activities recently.

Psychological – external motivational cues: The exercise tests performed in this study are symptom-limited, i.e., the subject will stop exercising when no longer able to tolerate the discomfort associated with the exercise. As such motivational cues provided to the subject can have profound effects on exercise performance. It is imperative that external motivational cues are controlled across subjects.

Time of exercise: No visual cues regarding the time of exercise should be provided to the volunteer. The subject's watch should be removed prior to exercise, and all other timekeeping devices (i.e., study staff watches, wall clocks, stopwatch, etc.) should be kept away from the volunteer's view.

Verbal encouragement: The wording and intensity of verbal encouragement provided to the subject will be standardized. Verbal encouragement will only be provided by one member of the study team, who is blinded to the results of the lung function tests. The tone of the encouragement should be enthusiastic and supportive, but not overbearing, overly loud or coercive in nature. Examples would be: "good work", "well done", "excellent job so far", "keep up the good work". Reinforcement could also consist of "that's a good pedaling rate" or if the pedaling rate is dropping you could try a positive reminder "keep up the pedaling rate – that's great". You may reinforce a little regarding the IC maneuver as well, i.e., "that was a good one" or use constructive criticism if it wasn't, i.e., "that was good, but maybe next time try to...".

Comfort with equipment: Subjects should be instructed to bring appropriate dress for exercise (i.e., shorts or track pants, gym shoes, T-shirt or sweat shirt) when reporting in to the study center on Study Day –1 of Period I and II. This attire should be worn for the exercise test, and study staff should ensure that the volunteer is comfortable with the mouthpiece and the positioning of other equipment prior to starting the exercise.

Familiarity with test: Before starting exercise, a member of the study team should make sure that the subject is completely familiar with the type of exercise that is to be performed; for the incremental test, subjects should be told that the test will feel like he/she is cycling up a hill and that each minute the slope of the hill will increase; for the constant work rate test, subjects should be told that the test will feel like he/she is cycling up a hill with a constant slope. It is important that the subject understands the difference between the incremental test and constant work rate test

Understanding "exercise for as long as you can": It is extremely important that the subject understands that there is no specific time limit to any of the exercise tests, and that the test will continue as long as the subject is able to. Stress to the subjects that the study team will not stop the test unless there is concern for the subject's safety, or the subject is unable to maintain the required pedaling frequency.

The cycle exercise test will be captured on the pCRF in four categories: predicted, baseline, maximum exercise and % predicted. Each category will include (as appropriate): work load (watts), VO_2 (L/min), VCO_2 (L/min), RQ, HR (BPM) O_2 pulse (mL/beat), systolic BP

(mmHg), diastolic BP (mmHg), VE-Norm Pred, VE-BTPS (L/min), RR (BPM) VD/VT-ABG(%), V_t (Liters), FIO₂(%), SPO₂(% and SaO₂(%).

4.4 Safety measurements

Please refer to the study plans in Table 1 through Table 3 for the precise timing of safety measurements.

4.4.1 Demographics and informed consent

The subject's signed and dated informed consent form must be obtained before conducting any procedure specifically for the study (Refer to Section 7.3). Demographics (date of birth, sex, race, date of signed informed consent) for each subject will be obtained and collected on the appropriate CRF, whether or not they are entered into the study.

4.4.2 Inclusion and exclusion criteria

The inclusion and exclusion criteria must be assessed and reviewed with each subject at the screening visit, Day -1 of Periods I and II in order to establish and confirm their eligibility to participate in the study.

4.4.3 Medical history

A detailed medical history including surgical and medication histories will be recorded for each subject at the initial screening visit and updated at admission on Day -1 of Periods I and II. Significant medical conditions that have occurred within the past 2 years or conditions that are ongoing (i.e., headache, backache, indigestion) are to be recorded in the appropriate pCRF.

The medication history must identify any known drug allergies, presence or history of drug abuse and use of chronic medications. All medications and over-the-counter (OTC) products (including vitamins and herbal products) taken within 2 weeks before Day -1 of Period I are to be recorded on the pCRF.

4.4.4 Laboratory safety measurements

Blood and urine samples for determination of clinical chemistry, hematology and urinalysis parameters will be taken at the times given in the study plan (Table 1). The date and time of collection will be recorded on the appropriate pCRF.

The following laboratory variables will be measured:

Periods I and II

Clinical chemistry	Hematology	Urinalysis
Calcium	Hemoglobin	Specific gravity
Glucose	Hematocrit	PH
Total bilirubin	Erythrocytes (RBCs)	Glucose
Alkaline phosphatase	Leukocytes (WBCs)	Ketones
Creatinine	Platelet count	Protein
Total protein	Red cell distribution width	Bilirubin
Albumin	Mean corpuscular volume	Occult blood
Aspartate aminotransferase	Mean corpuscular hemoglobin concentration (MCHC)	Microscopic analysis of formed elements ^a
Alanine aminotransferase	Differential leukocytes including:	
Sodium	Lymphocytes	
Potassium	Basophils	
Magnesium	Monocytes	
Phosphate	Neutrophils	
Blood urea nitrogen	Eosinophils	
Chloride		
Uric acid		
Gamma glutamyl transpeptidase		
Creatine kinase (CK)		

^aIf a urine sample is positive for protein or blood, a microscopic examination of the urine sediment will be performed.

If any of the tests performed on the samples taken after investigational product administration show clinically abnormal results as judged by the investigator, new blood samples will be taken and repeated until the results return to baseline or the cause is assessed. The investigator will provide an evaluation of the clinical importance of the deviation. The development of any clinically relevant deterioration in any laboratory test may constitute an AE if it leads to discontinuation of the study drug or if it fulfills the criteria of seriousness.

If ALT, AST, or bilirubin elevations are $\geq 3 \times$ ULN at any time, AstraZeneca should be informed immediately.

4.4.5 Urine drug screen

Urine will be tested for the following drugs of abuse: benzodiazepines, cocaine and/or metabolites, amphetamines, tetrahydrocannabinol (THC), opiates, methamphetamines (including ecstasy), phencyclidine (PCP), and barbiturates.

If a subject tests positive for drugs of abuse they will be excluded from entering, or continuing in, the study. If the drug is illegal, advice will be offered and the subject will be removed from the AstraZeneca Volunteer Panel.

4.4.6 HIV and hepatitis screens

Testing for the HIV antibody, HBsAg, and Hepatitis C antibody is to be performed on all subjects at screening only. If a test result is positive, the subject will not be allowed to proceed in the study.

Note: Although the results of the HIV and hepatitis screens must be documented in the subject's files, they will not be collected on the pCRFs and will therefore not be recorded in the study database.

4.4.7 Breath ethanol testing

Breath ethanol will be measured at the times specified in Table 1 and Table 2. If the result is positive, the subject will not be permitted to proceed in the study.

4.4.8 Electrocardiographic measurements

For timing of individual measurements refer to study plans Table 1 and Table 2.

4.4.8.1 Resting 12-lead ECG

Twelve-lead ECGs will be obtained after the subject has been lying down for 5 minutes in each case.

4.4.9 Vital signs

Vital signs assessments in addition to those discussed below can be made at the discretion of the investigator in order to follow the subject's clinical condition. These assessments should be entered as unscheduled assessments in the appropriate sections of the pCRF.

4.4.9.1 Blood pressure and heart rate

Blood pressure and heart rate will be measured with an appropriate cuff size after the subject has been sitting for at least 5 minutes. As much as possible, for each subject throughout the study, blood pressure should be measured using the same arm.

For timing of individual measurements refer to Table 1 and Table 2.

4.4.9.2 Respiratory rate

One minute respiratory rate will be assessed after the subject has been sitting for 5 minutes. Refer to Table 1 through Table 3 for the timing of individual measurements.

4.4.9.3 Oral temperature

Oral temperature will be measured in degrees Celsius (°C).

4.4.10 Height and weight

Height (cm) and weight (kg) will be measured without shoes.

4.4.11 Physical examination

4.4.11.1 Complete physical examination

The complete physical examination will include an assessment of the following: general appearance, skin, head and neck (including eyes, ears and throat), lymph nodes, thyroid, musculoskeletal/extremities (including spine), cardiovascular, lungs, abdomen, and neurological systems.

Complete physical examination data to be recorded on the pCRF will include: 1) normal/abnormal, and 2) a description of any abnormalities. Except for the screening examination, if there has been no change from the previous exam, only that information need be recorded.

4.4.11.2 Brief Physical Examination

The brief physical examination will include an assessment of the following: abdomen, lungs, and the cardiovascular system.

Brief physical examination data to be recorded on the pCRF will include: 1) normal/abnormal, and 2) a description of any abnormalities. If there has been no change from the previous exam, only that information need be recorded.

4.5 Genetic measurements and co-variables

4.5.1 Collection of samples for genetic testing

Subjects will provide a blood sample as per the inclusion criteria and visit schedule.

A single venous blood sample (9 mL) will be collected into a polypropylene tube containing ethylenediamine tetra-acetic acid (EDTA) and gently inverted a minimum of five times to mix thoroughly. Tubes will be labeled with the protocol study number, centre number, enrollment code and/or randomization number and date of sample collection. No personal identifiers (subject name, initials or date of birth) will be placed on the tube or accompanying documentation. A record of the date of the subject consent to the genetic research and the date of the blood sample collection will be recorded in the appropriate section of the CRF.

Genotype is a stable parameter, therefore if for any reason the blood sample is not drawn at Visit 2, it may be taken at any visit until the last study visit. The genetic blood sample should ideally be drawn through the same cannula used to draw blood samples required for the main study.

4.5.1.1 Sample processing and shipping

Samples will be frozen (-20°C or below) and transported to the relevant DNA extraction laboratory within one month of collection and must remain frozen at all times.

Where possible samples should be shipped in batches and shipment should be coordinated with the receiving site to ensure that samples arrive within working hours. A requisition sheet, detailing the protocol study number, centre number, enrollment code and/or randomization number and date of sample collection, should accompany the shipment.

4.5.1.2 Storage and coding of DNA samples

The processes adopted for the coding and storage of samples for genetic analysis are important to maintain subject confidentiality.

For all samples irrespective of the type of coding used the DNA will be extracted from the blood sample. The DNA sample will be assigned a unique number replacing the information on the sample tube. Thereafter, the DNA sample will be identifiable by the unique DNA number only. The DNA number will be used to identify the sample and corresponding data at the AstraZeneca genetics laboratories, or at the designated contract laboratory. No personal details identifying the individual will be available to any AstraZeneca employee working with the DNA.

The blood samples and data for genetic analysis in this study will be coded. Each blood sample will be labelled with the study number and subject number. Only the investigator will be able to link the blood sample to the individual subject. The sample and data will not be labelled with a personal identifier. The link between the subject enrollment/randomization code and the DNA number will be maintained. The link will be used to identify the relevant DNA samples for analysis, facilitate the correlations of genotypic results with clinical data, allow regulatory audit and to trace samples for destruction in the case of withdrawal of consent.

All DNA samples will be stored under secure conditions with restricted access at AstraZeneca. The blood, DNA samples or data derived from the samples may be made available to groups or organisations working with AstraZeneca on this study or as part of the development drug project. However, the samples and any results will remain the property of AstraZeneca at all times. AstraZeneca will not give blood, DNA samples or data derived from the samples to any other parties, except as required by law.

Samples will be stored for a maximum of 20 years, from the date of completion of the study, after which they will be destroyed.

DNA is a finite resource that is used up during analysis. Samples will be stored and used until no further analyses are possible. Further samples will not be acquired from subjects.

4.5.1.3 Summary of genetic assessments and analysis

The purpose of the genetic component of the study is to generate data for use in future retrospective analyses. Future analyses will explore genetic factors which may influence the absorption and disposition of, and response to AZD6140. The results of the genetic analyses will not form part of the clinical study report for this study. The results may be pooled with genetic data from other studies on AZD6140 to generate hypotheses to be tested in future studies.

4.6 Volume of blood sampling

The total volume of blood that will be drawn from each subject in this study is as follows:

Table 6 Volume of blood to be drawn from each subject

Assessment	Sample volume (mL)	n of samples	Total volume (mL)
AZD6140 PK samples	2 mL	17	34 mL
Arterial blood gas ^a	1 mL	1	1 mL
Blood Sample for genotyping ^b	9 mL	1	9 mL
Safety	Clinical chemistry	7	70 mL
	Hematology	7	35 mL
Screening	Clinical chemistry	1	10 mL
	Hematology	1	5 mL
	HIV/HBsAg, hepatitis C	1	10 mL
Total			174 ML^c

a. To be collected only if a subject experiences a spontaneous dyspnea episode

b. A separate informed consent required.

c. Total blood volume may vary if subject experiences a spontaneous dyspnea episode, which requires both an ABG (1 mL) and PK (2 ML) sample(s) to be drawn.

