The optional genetic sampling will be taken from subjects who have signed a separate consent form for genetic analysis on Study Day 1 prior to dose administration (Period I only). Blood samples for the determination of AZD6140, and its metabolite AR-C124910XX, in plasma will be collected on Study Days 1, 2, 3 and 4 in each treatment. Refer to Table 2 , Table 3 and Sections 4.3 and 4.4 for the timing and detailed descriptions of all the study procedures and assessments to be performed in each treatment.

If a subject experiences a spontaneous dyspnea episode any time throughout the inpatient study period (beginning with first dose administration), specific study procedures need to be completed sequentially as described in Table 3. These procedures should be completed at the onset of each dyspnea episode with the exception of an occurrence during cycle exercise testing.

If a dyspnea episode manifests intermittent symptoms within short time intervals (hours), generally if symptoms are similar and no initial abnormalities are observed on assessments, repeat assessments may be performed as needed at the investigator's judgement to monitor the subject's condition. Other diagnostic studies, such as echocardiogram or chest x-ray, may be performed to evaluate dyspnea at the investigator's discretion.

If a dyspnea episode subjectively worsens, assessments should be repeated at the investigator's discretion. The subject's dyspnea should resolve, or return to subject's baseline, before subject proceeds on to Period II (see Section 3.3.5.1).

Subjects will be discharged from the study center on Study Day 5 , after the completion of all protocol-driven procedures and assessments and at the discretion of the investigator. At discharge, subjects will be reminded of the study restrictions listed in Section 3.3.4 and instructed when to return for admission to Period II.

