3.1.3 Washout Period

There will be an outpatient washout period of 7 - 10 days between Periods I and II. The washout period will be counted starting from Study Day 5 of Period I.

3.1.4 Period II/Visit 3

Each day will be based on a 24-hour clock beginning at midnight (00:00).

Subjects will be admitted to the study center on Study Day -1 and will reside in the study center from Study Day-1 until completion of all protocol-driven procedures and assessments on Day 5 of Period II. The assessments on Day -1 of Period II, will reconfirm subject eligibility to participate in the study.

Subjects will crossover to receive the alternate treatment (Treatment A or B) given in Period I as described in the previous Section 3.1.2.

Subjects will be discharged from the study center on Study Day 5, after the completion of all protocol-driven procedures and assessments and at the discretion of the investigator. At discharge, subjects will be reminded of the study restrictions listed in Section 3.3.4 and instructed when to return for the follow-up visit.

3.1.5 Follow-up/Visit 4

Subjects return to the study center for the Follow-up Visit within 4 - 7 days of Study Day 5 of Period II. Please refer to Section 4.1.2 and Table 1 for the procedures and assessments to be completed at the Follow-up Visit.

Figure 1 Study Flow Chart

[figure not shown]

Table 1 Overall Study Plan

Study Assessment	Visit 1 ^a Screening	Visit 2 Period I	Visit 3 ^b Period II	Visit 4 ^c Follow-up
Informed consent ^d	X			
Demographics	X			
Inclusion/exclusion criteria	X	X	X	
Medical/surgical history	X			
Clinical laboratory assessments	X	X	X	X
Urine drug screen	X	X	X	
HIV antibody & hepatitis B and C screens	X			
Breath ethanol test		X	X	
Oral temperature	X	X		X
BP and pulse	X	X	X	X
Height and weight	X			X ^e
Complete physical examination	X			X
Brief physical examination		X	X	
12-lead ECG	X	X	X	X
Genetic blood sample ^{d, f}		X		
Inpatient stay		X	X	
Randomization ^f		X		
AZD6140 or placebo administration		X	X	
AZD6140/AR-C124910XX PK blood samples		X	X	
Modified Borg Scale/Bidirectional Dyspnea Index ^g	X	X	X	
Minute ventilation (including respiratory rate) ^g	X	X	X	
Spirometry(FEV ₁ , FVC) ^g	X	X	X	
Cardiopulmonary exercise test ^g		X	X	
Arterial blood gas ^h		X	X	
Pulse oximetry		X	X	
Concomitant medication monitoring	X	X	X	X
Adverse event monitoring ⁱ	X	X	X	X

- a. Within 21 days of Day 1, Period I.
- b. There will be a 7–10 day washout period between Period I and Period II.

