4.2.1 AZD6140 and AR-C124910XX

4.2.1.1 Determination of drug concentration in biological samples

Samples for measurement of drug concentration of AZD6140 and its metabolite, AR-C124910XX, in plasma will be analysed by York Bioanalytical Solutions, Upper Poppleton, York, UK using fully validated bioanalytical methods. Details of the methods used will be provided in the clinical study report (CSR). Samples will be disposed of after the CSR has been finalized.

4.2.1.2 Collection and processing of biological samples for determination of AZD6140/AR-124910XX in plasma

Venous blood samples (2 mL) for determination of AZD6140 and AR-C124910XX concentrations in plasma will be taken at the times presented in Table 2, Table 3 and Table 5. Blood samples will be collected, labelled and shipped as detailed below. The date and time of collection will be recorded on the appropriate CRF.

Blood will be collected according to site procedure. Disposable needles and disposable and lithium heparinized tubes shall be used. Individual venipunctures for each time point may be performed or an indwelling catheter may be used. Between two consecutive blood samples, the IV cannula of the catheter will be closed using a single-use stylet to avoid the use of saline and from discarding any blood. Blood samples (2 mL) will be collected into a lithium-heparinized tube. The heparin and blood will be carefully mixed. The sample will be placed on ice until centrifugation, which will begin within 30 minutes after the sample is obtained.

The sample will be centrifuged for 10 minutes at 4°C at a relative centrifugal force of 1500g. The resulting plasma will be transferred to a 2.0 mL conical polypropylene tube with screw cap and immediately frozen upright at -20°C or below in a non frost-free freezer and kept frozen at this temperature before, during and after transport to the designated laboratory.

Samples should be stored at -20°C or below and analysed within the timeframe after collection for which the stability in the samples has been validated and found acceptable. Results from analyses stored longer than the period stated will not be reported.

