4.2.1.3 Labelling of AZD6140 and/AR-C124910XX plasma samples for shipment to AstraZeneca

The labels supplied by AstraZeneca R & D Wilmington, DE must be applied to the plasma sample tubes. The labels should include the following information for the *scheduled PK samples* in Periods I and II:

Study number: D5130C00028

Subject number:

Tube number:

Period I or II/Study day:

Scheduled time:

Analyte: AZD6140/AR-C124910XX

Matrix: PLASMA

Table 5 Schedule of AZD6140/AR-C124910XX PK blood sampling and tube numbers

Periods I and II			
Study Day	Analyte	Scheduled Time Relative to Dose (Hours)	Tube Number
Day 1	AZD6140/AR-C124910XX	Predose*	1
	AZD6140/AR-C124910XX	2	2
	AZD6140/AR-C124910XX	3	3
	AZD6140/AR-C124910XX	4	4
	AZD6140/AR-C124910XX	8	5
	AZD6140/AR-C124910XX	12*	6
Day 2	AZD6140/AR-C124910XX	0*	7
	AZD6140/AR-C124910XX	3	8
Day 3	AZD6140/AR-C124910XX	0*	9
	AZD6140/AR-C124910XX	3	10
Day 4	AZD6140/AR-C124910XX	0*	11

Periods I and II			
Study Day	Analyte	Scheduled Time Relative to Dose (Hours)	Tube Number
	AZD6140/AR-C124910XX	2	12
	AZD6140/AR-C124910XX	3	13
	AZD6140/AR-C124910XX	4	14
	AZD6140/AR-C124910XX	8	15
	AZD6140/AR-C124910XX	12	16
Day 5	AZD6140/AR-C124910XX	0	17

- Blood sample must be drawn prior to dose administration.

The labels for *unscheduled PK samples* collected during a spontaneous dyspnea episode will include the following information:

Study number: D5130C00028

Subject number:

Period I or II/Study Day:

Collection time:

Analyte: AZD6140/AR-C124910XX

Matrix: PLASMA

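### Table 6 counts the 17 PK samples of one period only, so the stated 174 mL of blood per subject should read 208 mL

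*Protocol*

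**What the plan says.** Protocol Section 4.6 presents Table 6 as a whole-study figure for each subject: "The total volume of blood that will be drawn from each subject in this study is as follows". Its PK row reads "AZD6140 PK samples 2 mL 17 34 mL", and the table total is 174 mL. The footnotes say that the arterial blood gas sample is conditional ("To be collected only if a subject experiences a spontaneous dyspnea episode"), that genotyping needs separate consent, and that the total may vary with dyspnea episodes.

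The PK schedule is set out in four other places:

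- Table 5 in Section 4.2.1.3, titled "Schedule of AZD6140/AR-C124910XX PK blood sampling and tube numbers", numbers the tubes 1 to 17 over Days 1 to 5. Its column heading covers Periods I and II. The label instructions that precede it refer to "scheduled PK samples* in Periods I and II" and require the period to be written on each tube.
- Table 1 has the row "AZD6140/AR-C124910XX PK blood samples X X", with the marks under Visit 2 (Period I) and Visit 3 (Period II).
- Table 2 gives one schedule for both periods.
- Section 3.1.2 says that samples for parent drug and metabolite "in plasma will be collected on Study Days 1, 2, 3 and 4 in each treatment".

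**The concern.** Table 6 claims to cover the whole study, yet its PK count equals the number of tubes in one period of a two-period crossover. If the same 17 tubes are filled in each period, the PK row is half what it should be and the total is too low by the same amount.

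This is a matter of accurate disclosure. Table 6 is where the protocol states the total blood volume per subject. Section 7.1 sends the protocol for ethics approval, and Section 7.3 requires that subjects be fully informed. The row that is too low is also the most frequent draw: 17 scheduled collections per subject are left out.

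**Working it through.** **Step 1. Reproduce the stated total.** The rows of Table 6, in mL, are: PK 34, arterial blood gas 1, genotyping 9, safety chemistry 70, safety hematology 35, screening chemistry 10, screening hematology 5, and viral screens 10.

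34 + 1 + 9 + 70 + 35 + 10 + 5 + 10 = 174 mL

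The addition is right. Any error must lie in a row.

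**Step 2. Count the PK samples per period from Table 5.** Day 1 has 6, Day 2 has 2, Day 3 has 2, Day 4 has 6 and Day 5 has 1.

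6 + 2 + 2 + 6 + 1 = 17 per period

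This is exactly the count in the PK row of Table 6.

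**Step 3. Apply the schedule to both periods** (Tables 1, 2 and 5; Section 3.1.2), with 2 mL per sample (Section 4.2.1.2).

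2 periods × 17 samples = 34 samples; 34 × 2 mL = 68 mL

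**Step 4. Test whether Table 6 could be a per-period table.** It lists 7 safety draws each for chemistry and hematology, with screening on separate rows. Table 2 marks 3 laboratory assessments per period, and Table 1 adds one at follow-up.

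3 × 2 + 1 = 7

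The safety rows therefore span both periods. With one period only there would be 3 + 1 = 4 draws. At 70/7 = 10 mL for chemistry and 35/7 = 5 mL for hematology, the total would be:

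34 + 1 + 9 + 40 + 20 + 25 = 129 mL

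This is not 174 mL, so the per-period reading fails.

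**Step 5. Corrected total on the table's own basis.**

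68 + 1 + 9 + 70 + 35 + 10 + 5 + 10 = 208 mL

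Difference: 208 − 174 = 34 mL. Relative to the stated figure, 34/174 = 19.5%. Put the other way, the stated figure is 34/208 = 16.3% below the corrected one.

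**Step 6. Remove the samples that not every subject gives.**

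| Basis | As printed (mL) | Corrected (mL) |
|---|---|---|
| All rows of Table 6 | 174 | 208 |
| Without arterial blood gas (1 mL) | 173 | 207 |
| Without blood gas and genotyping (1 + 9 mL) | 164 | 198 |

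The gap is 34 mL on every basis.

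**The case against.** The strongest case on the other side is that the slip is clerical and small. Section 4.2.1.2 directs sampling to Tables 2, 3 and 5, not to Table 6, so conduct would not change. No objective, endpoint, analysis set or sample-size statement depends on the figure. The protocol sets no blood-volume limit that 208 mL would breach and 174 mL would not, and the extra 34 mL is spread over about 45 days of participation. Nothing in the protocol links that volume to a hazard. The consent form is not available here, so it is unknown whether it repeats 174 mL. All of this stands, and it limits the weight of the point.

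Three narrower objections are also fair, but they do not alter the result:

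- The 208 mL includes the conditional blood gas and the optional genotyping sample. So does the 174 mL, so the two figures are comparable.
- Only the two safety laboratory rows span both periods. Screening and genotyping are done once, and one blood gas is counted. The safety rows alone are enough to rule out a per-period reading.
- Section 3.1.2 names Days 1 to 4 only, which in Table 5 gives 16 samples. The 17th is the Day 5 tube. Section 3.1.2 supports sampling under both treatments, and the count of 17 rests on Table 5.

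Two possible rescues fail. No section confines PK sampling to the active period, and under the blinding in Section 3.4.4.1 study staff would not know which period that is. Footnote c of Table 6 allows only for extra samples at dyspnea episodes, not for 17 scheduled ones.

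**Conclusion.** The concern holds. Table 6 adds up correctly, but its PK row covers one period while its safety laboratory rows cover two. A subject who completes both periods has 34 scheduled PK samples (68 mL), and the total is 208 mL, which is 34 mL or 19.5% above the stated 174 mL.

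The result rests on the 17 tubes of Table 5 being collected in each period, which Table 1 and Section 3.1.2 confirm. The PK row of Table 2 could not be matched cell by cell to its column headings in the copy read, so Table 5, whose count Table 6 shares, is the basis. The 3 safety draws per period are read from the marks in Table 2 and agree with the 7 in Table 6.

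This is a wrong figure for subject burden that should be corrected. It has no bearing on the statistical analysis.

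**What to change.** In Table 6, change the PK row to 34 samples and 68 mL, and the total to 208 mL. Alternatively, show the PK samples as 17 in each period with both periods entered, so that the count can be traced to Table 5. The existing footnotes can stay as they are. Check whether the consent form and the ethics submission quote 174 mL, and align them if they do.

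The cost is one table row, one total and that check. No procedure, visit or analysis changes; the stated burden simply becomes somewhat higher.
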